Over the last 3 years, the ENLIVEN (Endoscopic Lavage after Intraventricular Haemorrhage in Neonates) pilot study at Great Ormond Street Hospital (GOSH) has been randomly assigning preterm infants with PHVD to VSGS with NEL or VSGS alone (26). Between January 2018 and January 2022, 17 infants have been enrolled in this single centre pilot study. This represents two thirds of the admissions to the service for treatment of PHVD, establishing that recruitment is feasible and that parents are willing to enrol their child. NEL was carried out with an endoscope on the side of the greater blood load. The study was powered to detect a reduction in the need for VP shunt insertion at 6 months. To date we have seen no difference in the primary outcome in this small number of patients. Infants who underwent lavage were less likely to require tapping or revision of their VSG shunt, suggesting that the overall reduction in the amount of blood and debris in the CSF by the irrigation reduced the risk of VSG shunt blockage. The median body weight at NEL in this patient group was 886g; although this was lower than in the published studies described above, there have been no safety concerns.

The above evidence makes a compelling case to undertake a large multi-centre randomised controlled trial of NEL in the UK to assess efficacy and safety.

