1.2 Objectives

The objective of this study is to establish the efficacy and safety of the addition of NEL to standard care during temporising device insertion. It is hypothesised that the addition of NEL will be safe and will improve neurodevelopmental outcomes at 2 years in children with severe IVH and PHVD.

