5.1.2 Secondary Outcomes

The secondary outcome measures are:

- 1. Developmental Measures:
 - a. Motor quotient (MQ): Age equivalent motor score of the Bayley IV divided by corrected age at assessment, measured at 2 years' corrected age
 - b. Language quotient (LQ): Age equivalent language score of the Bayley IV divided by corrected age at assessment, measured at 2 years' corrected age
- 2. Other neurological and functional assessments conducted during the 2-year follow-up visit:
 - a. Presence of seizures during the first 2 years and use of anticonvulsant medication at 2 years.
 - Presence of cerebral palsy (+ accompanying Gross Motor Function Classification System (GMFCS) grade and deficit distribution map using the Classification of SCPE
 - c. Assessment of hearing and vision (British Association of Perinatal Medicine classification)
 - d. Parent report:
 - i. Brief Infant Toddler Social Emotional Assessment (BITSEA)
 - ii. Quantitative Checklist for Autism in Toddlers (Q-CHAT)
- 3. Mortality up to 2 years corrected age.
- 4. NEL & VP shunt related outcomes:

- a. Safety of NEL: Number of Adverse Events, where Adverse Events would include (and not limited to) secondary bleeding in the brain, post-operative infections, temporising device survival, mortality, stroke, seizures, electrolyte disturbances, CSF leak, unexpected readmissions or return to theatre.
- b. Number and type of further surgical procedures, including revision of the temporising drainage device (VAD or VSG), addition of a second temporising device, surgery for loculated or isolated ventricles, and revisions of the VP shunt, if implanted, until two years' corrected age. These infants often need multiple shunt revisions during their first two years of life. We will have a separate CRF to record data related to these unexpected presentations and procedures.
- c. Requirement for permanent VP shunt insertion at 6 months' corrected age. (This is at the discretion of the treating team in the participating centre, according to routine clinical care).
- 5. Quality of life and health economic assessments:
 - a. Health-Related Quality of Life (HRQoL) in children: TNO-AZL Preschool Children's Quality of Life (TAPQOL) to be assessed at 12-months and 2 years' corrected age
 - b. HRQoL in primary caregiver: EuroQoL EQ-5D-5L to be assessed at baseline, 6 months, 12 months- and 2 years' corrected age

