6.1.1 Adverse Events

Adverse events include:

- an exacerbation (i.e., increase in the frequency or intensity) of a pre-existing illness, episodic event or symptom (initially recorded at the screening/baseline visit), that is detected after trial intervention
- occurrence of a new illness, episodic event or symptom, that is detected after trial intervention

Adverse events do NOT include:

- Medical or surgical procedures: the condition that leads to the procedure is the adverse event
- Pre-existing disease or a condition present before treatment that does not worsen
- Hospitalisation where no untoward or unintended response has occurred

Reporting of Adverse Events

The patient population includes preterm infants who are cared for on a neonatal intensive care for a prolonged period. Due to the nature of the patient population, a high incidence of adverse events can be foreseeable during their hospital stay. Only adverse events deemed as serious (see section 6.1.2) or as notifiable event (see section 6.2) will be recorded for the trial.

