6.1.2 Serious Adverse Events

6.1.2.1 Foreseeable (expected) SAEs

The following are 'Foreseeable SAEs' that could be reasonably anticipated to occur in this population of infants during the course of the trial or form part of the outcome data.

They do not require expedited reporting by trial centres as SAEs **unless considered causally related** to the intervention (NEL) in which case they should be reported within 24 hours of site staff becoming aware of them as detailed in section 6.3.2.

'Foreseeable SAEs' that are **casually related** to the trial intervention (NEL) should be reported within 24 hours of site staff becoming aware of them using the SAE report form.

Foreseeable SAEs that are **not considered causally related** to the trial intervention (NEL) should be reported within 5 working days. Therefore, all Foreseeable SAEs occurring for patients in Arm B (Temporising device alone) will be not related to NEL and should be reported within 5 days.

Foreseeable SAEs:

- Necrotising enterocolitis or gastrointestinal perforation
- Intracranial abnormality (intraventricular haemorrhage or white matter damage) on cranial ultrasound scan or other imaging
- Seizures outside of 48 hours the procedure
- Pulmonary hypertension
- Hydrocephalus
- Respiratory distress syndrome
- Bronchopulmonary dysplasia or chronic lung disease
- Retinopathy of prematurity
- Early or late-onset Sepsis
- Patent ductus arteriosus (PDA)
- Pulmonary haemorrhage
- Pneumothorax
- Anaemia
- Hyperbilirubinaemia/jaundice
- Hypoglycaemia
- Hyperglycaemia
- Coagulopathy
- Liver cholestasis
- Liver failure
- Hypotension
- Hypertension
- Impaired renal function
- Extravasation injury
- Fractures
- Return to hospital for suspected or actual shunt malfunction or other neonatal condition unrelated to hydrocephalus after discharge from the neonatal unit, (unless readmission following initial discharge from hospital for grade 3 and above events)

6.1.2.2 'Unforeseeable SAEs' – (All SAEs not listed as 'Foreseeable SAEs')

All other SAEs occurring in trial participants which are not listed as Foreseeable SAEs in Section 6.1.2.1 are classed as unforeseeable SAEs and must be reported immediately after site staff become aware of the event (in no circumstances should this notification take longer than 24 hours) (see section 6.3).

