6.4.2 Notifications

6.4.2.1 Notifications by the Investigator to CCTU

CCTU must be notified of all SAEs excepting those listed in 6.1.2.1 - unless considered **causally related** to the intervention immediately after site staff become aware of the event (in no circumstances should this notification take longer than 24 hours).

The Foreseeable (expected) SAEs listed in section 6.1.2.1 must be reported within 24 hours of site staff becoming aware of them **if they are considered causally related** to the trial intervention (NEL).

'Foreseeable SAEs' that are **not considered causally related** to the trial intervention (NEL) should be reported within 5 working days using the SAE report form.

All 'Unforeseeable SAEs' i.e., all other SAEs occurring in trial participants which are not detailed in Section 6.1.2.1 should be reported within 24 hours of site staff becoming aware of them using the SAE report form.

All Notifiable AEs (NAEs) listed in Section 6.2 should be reported within 5 working days using the Notifiable Adverse Events (NAE) CRF.

Investigators should notify CCTU of any SAEs and Notifiable Adverse Events (NAEs) occurring from the time of randomisation until 2-year hospital visit follow up. From this point forward the site will not actively monitor SAEs or NAEs.

The SAE form must be completed by the site staff named on the delegation log with this responsibility assigned by the PI. The form should be reviewed and signed off by the investigator (listed on the delegation log) who is responsible for the participant's care with

attention paid to the grading and causality of the event. The responsible investigator should check the SAE form at the earliest opportunity, make any changes necessary and sign. Systems should be in place at the site to enable the investigator to check the form for clinical accuracy as soon as possible.

The minimum criteria required for reporting an SAE are the primary event term, participant's trial specific PIN, date of birth, name of reporting investigator and sufficient information on the event to confirm seriousness. Any further information regarding the event that is unavailable at the time of the first report should be completed as soon as it becomes available.

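### Outcome 4a measures the safety of NEL as an open-ended number of adverse events; reported as one number, it can dilute or offset a real rise in procedural harm

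*Protocol*

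**What the plan says.** Section 1.2 makes safety part of the objective: "It is hypothesised that the addition of NEL will be safe". The outcome that carries it is 4a in Section 5.1.2: "Safety of NEL: Number of Adverse Events, where Adverse Events would include (and not limited to) secondary bleeding in the brain". The list also names post-operative infections and continues "temporising device survival, mortality, stroke, seizures, electrolyte disturbances, CSF leak, unexpected readmissions or return to theatre". It gives no time window, no split by event type and no rule on attribution. The next item, 4b, asks for both the number and the type of further surgical procedures; 4a asks for a number only.

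Three other sections determine what feeds that number:

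- Section 6.1.1: "Only adverse events deemed as serious (see section 6.1.2) or as notifiable event (see section 6.2) will be recorded for the trial". The same section warns that "a high incidence of adverse events can be foreseeable during their hospital stay".
- Section 6.1.2.1 lists foreseeable SAEs that "could be reasonably anticipated to occur in this population of infants during the course of the trial", among them necrotising enterocolitis, bronchopulmonary dysplasia, retinopathy of prematurity and sepsis.
- Section 6.4.2.1 requires sites to report SAEs and notifiable events "occurring from the time of randomisation until 2-year hospital visit follow up".

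On the expected direction of device failure, Section 1.1.1 reports from the single-centre pilot of 17 infants: "Infants who underwent lavage were less likely to require tapping or revision of their VSG shunt".

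**The concern.** The items in 4a do not point the same way. A secondary bleed, a procedure-associated infection, a stroke, an early seizure or a CSF leak could rise with lavage. Device failure, and the returns to theatre it causes, may fall. Serious complications of prematurity should hardly respond to a procedure of about 30 minutes, but they can be numerous over two years. Adding these together loses information in two ways: unrelated events add noise (dilution), and a fall in one component offsets a rise in another (cancellation).

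Two items do not belong in such a count. Device survival is not an adverse event. Mortality has its own outcome, and an infant who dies early stops contributing further events.

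Restricting the count to events attributed to NEL would not help. Section 6.1.2.1 treats every foreseeable SAE in Arm B as unrelated to NEL by rule, so counts of related events are not comparable between arms.

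At stake is whether the safety half of the objective can be answered from its own outcome.

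**Working it through.** **The plan's own figure.** The protocol states no rate, effect size or power for 4a. Its only power statement (Section 8.1) concerns the primary outcome: 45 per arm, Beta(1,1) versus Beta(10, 4.25), two-sided 5% Wilcoxon test, 90% power. Simulation gives 0.913, and 90/(1 − 0.10) = 100, so it reproduces. It says nothing about safety.

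**Inputs for the illustration.** From the protocol: 50 infants per arm (Section 8.1). Assumed, because the protocol gives only an additional procedural risk under 5% (Section 1.4): a procedural event such as a bleed in 5% of control and 20% of NEL infants; device failures of 0.60 per infant in control and between 0.60 and 0.20 with NEL; background serious events of 1, 3 or 6 per infant, with and without overdispersion.

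**Expected difference in the total.** Per 50 infants it is 50 × [(0.20 − 0.05) + (device rate NEL − device rate control)].

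- Device rate 0.60 in both arms: 50 × 0.15 = +7.5 events.
- Device rate 0.60 versus 0.45: 50 × (0.15 − 0.15) = 0. A fourfold rise in procedural events disappears from the total.
- Device rate 0.60 versus 0.35: 50 × (0.15 − 0.25) = −5.0. The total favours NEL.

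**Why dilution matters without any device benefit.** Take 3 background events per infant (Poisson) and device rate 0.60 in both arms. Variance per infant is 3 + 0.60 + 0.05 × 0.95 = 3.65 in control and 3 + 0.60 + 0.20 × 0.80 = 3.76 with NEL. The standard error of the difference in means is √[(3.65 + 3.76)/50] = 0.385, so the standardised difference is 0.15/0.385 = 0.39. The chance of a significant result in the harm direction is P(Z > 1.96 − 0.39) ≈ 0.06. Simulation gives 0.060.

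**Simulated chance of flagging harm** (4,000 trials per case, two-sided 5%; ranges run over the background settings):

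| Procedural event, control vs NEL | Device failures per infant, control vs NEL | Total count flags harm | Procedural events compared directly (Fisher) |
|---|---|---|---|
| 5% vs 20% | 0.60 vs 0.60 | 4–7% | 51% |
| 5% vs 20% | 0.60 vs 0.45 | 2–3% | 51% |
| 5% vs 20% | 0.60 vs 0.35 | 1–2% | 51% |
| 5% vs 30% | 0.60 vs 0.60 | 4–15% | 90% |
| 5% vs 30% | 0.60 vs 0.35 | 2–3% | 90% |

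A second set of assumptions (5 overdispersed background events per infant, bleeds 5% vs 20%, revisions 0.4 vs 0.2) gives 2% for the total against about 50% for bleeds alone. The NEL total is equal to or below control in 51–54% of trials. With the device benefit removed, those figures become 44% equal or lower and 3.6% flagged. Most of the loss therefore comes from background noise, and cancellation adds to it.

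**Limit of direct comparison.** For 5% vs 10%, Fisher's test has about 6% power with 50 per arm. The standard error of that risk difference is √[(0.05 × 0.95 + 0.10 × 0.90)/50] = 0.052, so a 95% interval would run roughly from −5 to +15 percentage points.

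**The case against.** The best defence is that a single pooled total is only one reading of 4a. The outcome names event types after the word number. Section 8.3.7 promises methods suited to each measure's data structure and plots of the harm profile, and Section 8.3.1 leaves detail to a standalone SAP that is not shown here. A reader might infer that the protocol will test a pooled total and call NEL safe if the totals are similar. It states neither such a test nor such a rule, so that stronger reading is not supported.

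Procedural harm is also collected separately. Section 6.2 lists new bleeds, procedure-associated infection, early seizures and focal deficits, and returns to theatre. Under Section 6.5 the IDMC reviews SAEs, and every death case by case. These safeguards are real. They protect participants and make a by-type analysis possible, but they do not define the measure on which the arms are compared.

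Other limits also stand:

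- Not every condition listed in Section 6.1.2.1 counts. It must be serious, and a pre-existing condition that does not worsen is excluded by Section 6.1.1. The background load may be lower than assumed.
- Returns to theatre are not purely an efficacy matter. A return for infection or CSF leak is a possible harm of lavage. Readmissions are not listed in 4b.
- The expected device benefit rests on 17 infants.
- The count can also be biased against NEL: an abandoned NEL procedure is notifiable and can occur only in Arm A.

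**Conclusion.** The point holds in conditional form. Outcome 4a fixes the safety measure as an open-ended number that mixes possible procedural harms with mortality, device survival, device-related returns to theatre and serious complications of prematurity. If it is reported as one number, a real rise in procedural harm can be diluted or offset.

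The size cannot be derived from the documents. With bleeds assumed at 5% versus 20% and 50 infants per arm, the total flags harm in about 2–8% of trials when device failures are unchanged or just offset the extra bleeds, and less often if the device benefit is larger. Bleeds compared directly flag it in about 50%. A reader might take these figures as a forecast that harm will be cancelled out in this trial. They are not: every event rate is assumed, a 20% bleed rate lies well above the protocol's own expectation, and background noise drives much of the result.

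This should be corrected, because the objective includes safety and a better measure is available at little cost.

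**What to change.** Restate 4a as the number and proportion of infants in each arm with at least one event, by type, for the procedure-related events already named in 4a and Section 6.2: secondary bleed, procedure-associated infection, stroke, new seizure or focal deficit, CSF leak, and serious electrolyte disturbance. Count from the index surgery, with identical definitions and periods in both arms. Give a risk difference with 95% confidence interval for each type.

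Alongside this:

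- Reword items 5 and 6 of Section 6.2, which tie the 48-hour window to NEL, so that they refer to the trial procedure in either arm and capture Arm B events equally.
- Take temporising device survival and mortality out of 4a; report them under 4b and outcome 3.
- Keep return to theatre for infection or CSF leak visible as a safety event.
- Tabulate other SAEs and readmissions separately, by type, over the full follow-up.
- Use any early window (for example 30 days) only as an additional summary, so that later infections are not dropped.

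The cost is a revised outcome definition and a small change to the wording of safety recording. It is not wholly free: non-serious electrolyte disturbance is not currently recorded as an event, which is why only serious disturbance is listed. Power for small excesses stays low (about 6% for 5% versus 10%), so the safety conclusion should rest on estimates with confidence intervals, not on tests.

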5.2 Participant TimelineTable 1. ENLIVEN-UK Participant Schedule of Assessments

	Screening Visit ¹	Baseline Visit ³	Surgery (t=0)	Post- Operative Follow Up (t=24-48h)	First Clinical Follow Up (t=term equivalent	VP Shunt Insertion (if required)	3-6 Months Clinical Follow Up Visit	Age 1 Year Clinical Follow Up	18 Month Follow Up	2 Years corrected Age Clinical Follow Up	Unschedule d Visit to Neuro- surgical Unit ¹⁵
		Within 7 days prior to surgery (t=0)			+/- 1 month		+/- 2 months	+/- 2 months	+/- 2 months	+/- 2 months	
Informed consent	Х										
Eligibility ²	Х	х									
Papile grade		Х									
Birth Weight		х									
Cranial ultrasound ⁴		Х		Х		Х					
Haematology ⁵		Х		Х							
Biochemistry ⁶		Х		Х							
Coagulation/Clotting		х		х							
Imaging History ¹⁷		х									
Signs of raised ICP		х									
Randomisation			Х								
Physical Examination ⁸											х
Study Procedure (NEL+TD / TD alone) ¹¹			Х								

39

	Screening Visit ¹	Baseline Visit ³	Surgery (t=0)	Post- Operative Follow Up (t=24-48h)	First Clinical Follow Up (t=term equivalent	VP Shunt Insertion (if required)	3-6 Months Clinical Follow Up Visit	Age 1 Year Clinical Follow Up	18 Month Follow Up	2 Years corrected Age Clinical Follow Up	Unschedule d Visit to Neuro- surgical Unit ¹⁵
		Within 7 days prior to surgery (t=0)			+/- 1 month		+/- 2 months	+/- 2 months	+/- 2 months	+/- 2 months	
Discharge Information				х							
Head Circumference		х		Х	х	Х	х	х		Х	Х
Incidence of Seizures										Х	
Wound Site Check				Х	Х					Х	Х
CSF sample collection (optional) ¹⁶			Х			х					Х
Research Blood sample collection (optional) ¹⁶			Х			х					Х
Clinical Assessment ¹²		х		Х	Х	Х	Х	Х		Х	Х
Shunt/Temporising Device Information				х	Х	х	Х	Х		х	х
Adverse events Review			Х	X	Х	х	Х	Х	Х	х	Х
Concomitant Medication Review ¹³			Х	х	Х					х	
MRI (as per Standard of Care) ⁴					Х						Х
EuroQoL EQ-5D-5L ¹⁹		Х					X ¹⁸	Х		Х	
Adapted CSRI (children version)							Х	Х	Х	х	
TNO-AZL TAPQOL								Х		Х	
Bayley IV Scales ⁹										Х	

	Screening Visit ¹	Baseline Visit ³	Surgery (t=0)	Post- Operative Follow Up (t=24-48h)	First Clinical Follow Up (t=term equivalent	VP Shunt Insertion (if required)	3-6 Months Clinical Follow Up Visit	Age 1 Year Clinical Follow Up	18 Month Follow Up	2 Years corrected Age Clinical Follow Up	Unschedule d Visit to Neuro- surgical Unit ¹⁵
		Within 7 days prior to surgery (t=0)			+/- 1 month		+/- 2 months	+/- 2 months	+/- 2 months	+/- 2 months	
Cerebral palsy assessment 9, 10										Х	
Vision and hearing assessment (BAPM classification) ⁹										х	
Brief Infant Toddler Social Emotional Assessment (BITSEA)										х	
Quantitative Checklist for Autism in Toddlers (Q-CHAT)										х	

¹ Screening and baseline visit can occur on the same day if the infant's parent/guardian(s) have been given time to reflect on the information in the PIS and following a discussion with a medically qualified investigator where they have and been given the opportunity to ask questions.

Standard of care MRI scans may be submitted for review and storage for all infants where available and if performed as standard of care assessment only.

Please see Imaging Transfer Guidelines for further details.

² Review inclusion and exclusion criteria and ensure eligibility prior to enrolment and randomisation.

³ Baseline Visit assessments to confirm eligibility for trial should be performed within 7 days of Surgery (t=0). Baseline EuroQoL EQ-5D-5L Quality of Life questionnaire can be completed within 28 days prior to randomisation as it is not required to confirm eligibility.

⁴ Investigators are required to submit images of Ultrasound scans for review and storage for all infants.

⁵ Haematology – including Haemoglobin, White Blood Cell Count, platelets as per routine standard of care

⁶ Biochemistry – including Sodium, Potassium, as per routine standard of care

- ⁷ Coagulation: including INR or APTT as per routine standard of care
- ⁸ Physical Examination: Including heart rate, temperature, Glasgow Coma Score. Results of routine **Blood tests for Neutrophils Erythrocyte Sedimentation Rate and C-Reactive Protein should be collected if performed as part of routine care.**
- ⁹ Assessments will be performed by a qualified and validated independent clinical development specialist blinded to the treatment arm.
- ¹⁰ CP subtype (SCPE) & Gross Motor Function Classification System (GMFCS) grade will be assessed
- ¹¹ For Arm A (Intervention) patients, details of the NEL procedure will be recorded in addition to Temporising device information
- ¹² Clinical assessment including weight, review of parental concerns
- ¹³ Review of Concomitant medications for prophylactic antibiotics and anti-epileptic medications prescribed.
- ¹⁴ See section 5.2.1 for details about the performing the 2-year clinical follow-up visit
- ¹⁵ Unscheduled visits will be performed as deemed clinically necessary (i.e. all returns to the neurosurgical unit occurring in between scheduled visits until completion of 2-year follow-up)
- ¹⁶Research blood and CSF sample collection is optional. Please see Appendix 9 and the Laboratory Manual for further details.
- ¹⁷ Imaging History: Previous Imaging scans performed (including Ultrasound, CT and MRI)
- ¹⁸ Please ensure parent/guardian(s) are reminded to complete the EQ-5D-5L at 6-months. If the visit is scheduled earlier than 6 months, please ask parent/guardian(s) to take this questionnaire away for completion and return by post or at their next trial visit.
- ¹⁹ Responses to the EQ-5D-5L must be reviewed during the visit to check for parent/guardian self-reported 'severe' or 'extreme' anxiety and depression. Parents/guardians reporting these symptoms should be signposted to access support from their healthcare provider e.g., their GP.

5.2.1 2-years' corrected age Assessment

Table 2.

Table 2.	T =	
No. 14. N		cted age Clinical
Visit Name:	• • •	+/- 2 MONTHS)
	Independent	Completed at
	Blinded	Neurosurgical
Completed by:	Assessor	follow-up
Bayley IV Cognitive Quotient, Motor and Language		
Quotient	X	
Vision and hearing assessment (BAPM classification)	X	
Cerebral palsy assessment (SCPE & GMFCS)	X	
Clinical Assessment		Χ
Head Circumference		Χ
Incidence of seizure		Χ
Wound Site Check		Х
Shunt/Temporising Device Information		X
Review of AEs, NAEs and SAEs		X
Concomitant Medication Review		X
EuroQoL EQ-5D-5L*		X
Adapted Client Service Receipt Inventory (CSRI children		
version)		Х
TNO-AZL TAPQOL		X
Brief Infant Toddler Social Emotional Assessment		
(BITSEA)		X
Quantitative Checklist for Autism in Toddlers (Q-CHAT)		X

^{*}Responses to the EQ-5D-5L must be reviewed during the visit to check for parent/guardian self-reported 'severe' or 'extreme' anxiety and depression. Parents/guardians reporting these symptoms should be signposted to access support from their healthcare provider e.g., their GP.

